Acute alcohol is associated with increased cerebral blood flow (CBF). It is unknown if changes in CBF are due to alcohol, acetate, or both. Determining the differential effects of alcohol and acetate on brain function is significant as it could lead to new treatments targeting alcohol metabolites. The goal of the proposed study is to determine feasibility of measuring effects of oral alcohol and intravenous acetate on cerebral blood flow and function in moderate drinkers with the objective to use the data collected for an R01 or R21 application. Although currently there is no data in the literature on this, finding such changes would be important and could direct future prevention and treatment plans for alcohol use disorders. For this feasibility pilot study we propose to investigate the effects of acetate and alcohol on CBF and brain function with two specific aims.

Aim 1. Investigate the effects of acetate on cerebral blood flow and function in controls and AUD individuals

Preliminary data will be collected for the hypothesis that compared to placebo given IV acetate given IV will: a) increase CBF as measured by arterial spin labeling (ASL); and b) decrease blood oxygen level dependent (BOLD) activity during functional magnetic resonance imaging (fMRI); and c) these changes will be greater in AUD individuals than controls

Aim 2. Investigate the effects of alcohol on cerebral blood flow and function in controls and AUD individuals

Preliminary data will be collected for the hypothesis that compared to non-alcoholic jello shots, orally ingested alcohol jello shots will: a) increase CBF, and b) decrease BOLD activity; and c) these changes will be greater in AUD individuals than controls.

II. Background and Significance:

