Practice effects: It is possible that differences in brain activity could reflect learning effects. To test for learning effects we administered two versions of the decision-making task to a healthy control, 2 hours apart. The two versions differed in the color and position of the decks and the scale of the magnitude of outcomes, while keeping the value of the decks balanced. The frequency of wins and losses was identical. There was no difference in Play response on good cards (93 vs. 95), bad cards (54 vs. 55), or on net score (good minus bad cards played) (39 vs. 40). *This lack of significant practice effect is consistent with a prior study showing stable performance on the Iowa Gambling Task, on which our task is based, given multiple times to controls (Xiao et al., 2013) and patients (Waters-Wood et al., 2012) and, together, suggest that there will not be a significant learning effect.*

IV. Research Methods

A. Outcome Measure(s):

Our goal in this pilot study is feasibility.

Preliminary outcome measures:

1. CBF before and after acute alcohol or acetate
2. Brain activity during decision-making before and after acute alcohol or acetate

B. Description of Population to be Enrolled:

This is a single blinded placebo controlled test of the effects of acetate and alcohol on brain function.

Inclusions-all: (1) age 21-55, (2) English proficient, (3) Participants must understand the nature of the study and must sign an informed consent; (4) be currently non-smoking.

Inclusions-moderate drinkers: (1) participants must be moderate drinkers (male: 1-14 drinks per week; female: 1-7 drinks per week); and (2) have drunk at least 2 drinks in one hour in the past; and have no history of dependence on drugs or alcohol.

Inclusions-AUD: (1) must meet DSM-V criteria for lifetime history of Alcohol Use Disorder (AUD)

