E. Potential Scientific Problems:

1. Sex effects: Alcohol metabolism differs in men and women and several studies find an interaction between sex and alcohol's effect on terms of brain morphometry (Hommer et al., 2001), function, and CBF (Marxen et al., 2014; Rickenbacher et al., 2011). It should be noted, however, that not all studies have confirmed sex differences in brain morphometry (Demirakca et al., 2011). There will not be power to detect sex effects. Our goal is to demonstrate feasibility.

2. Vasomotor effect: The BOLD signal reflects complex interactions between CBF, cerebral blood volume, and oxygenation. We plan to study differences in global and regional vascular effects in acetate vs. alcohol treatment. The fMRI BOLD measurements are insensitive to time lags or shifts in the hemodynamic response of the brain during decision-making. Therefore in exploratory studies a finite impulse response (FIR) model will be used, according to prior work (Yamamoto et al., 2014).

3. Diurnal variations: We cannot exclude the possibility of diurnal fluctuations confounding our findings. The alternative to conduct blinded placebo and treatment studies on two separate days in the same participant would be a hardship on participants.

4. Dose-response: A dose-response for acetate or alcohol will not be obtained. Fortunately, the pharmacokinetics of alcohol are well established and the timing of the MR scans is planned according to Figure 2. The pharmacokinetics of acetate are not as well established. The IV infusion protocol will give us better control of plasma levels, and serum acetate and alcohol will be assayed.

F. Data Analysis Plan:

Blood alcohol and acetate: Levels of blood alcohol and acetate will be analyzed using colorimetric enzyme-linked immunosorbent assays (ELISA).

MR measures: MR CBF and fMRI BOLD activity data will be processed in SPM12 (The FIL Methods Group, 2014). First, each participants' T1-weighted anatomic image will be skull-stripped then coregistered to the Montreal Neurological Institute (MNI) MNI152 template. The transformation matrix generated from this step will be applied to CBF and BOLD contrast maps of interest.

MR CBF: Motion-corrected ASL CBF images (mL/100g/min) will be generated by the scanner software. CBF maps will be skull-stripped and co-registered to each participant's T1-weighted anatomic image in native space followed by application of the transformation matrix to MNI space.

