CBF: Whole brain analyses: The main effects of acetate on CBF will be analyzed in SPM12 using a repeated-measures ANCOVA with drug (alcohol, or acetate vs. placebo) as within-subject factor and adjusting for age and number of drinks per month. As this is a feasibility study, a less stringent threshold of $p < 0.05$, uncorrected will be used to explore for possible main effects and interaction effects as well as nonparametric approaches. In the later, larger study, significance levels will be set at $p < 0.05$, corrected for multiple comparisons with family-wise error (FWE) using AlphaSim Monte Carlo simulations, 10,000 iterations, to determine cluster size criterion. The voxel-level significance will be set at $p < 0.005$.

fMRI BOLD activity: ROI analyses: For each ROI and each subject, the percent signal change will be extracted using Marsbar toolbox. The feasibility analyses are the same as CBF: ROI approach. To provide context for this pilot, the statistical plan for the later, larger study is included: To examine the main effect of alcohol or acetate on BOLD response, a general linear multivariate model with 12 repeated BOLD response measurements as the outcomes will be employed. Covariates will include education level and number of drinks per week. From prior experience, BOLD activity during decision-making correlates with education level. Analyses are otherwise the same as CBF: ROI approach.

fMRI BOLD activity whole brain analyses: The feasibility analyses are the same as CBF: whole brain analyses. In the later, larger study, the main effects of alcohol or acetate on fMRI BOLD signal during decision-making will be analyzed in SPM12 using a repeated-measures ANCOVA with drug (alcohol or acetate vs. placebo) as within-subject factor and adjusting for education and number of drinks per month. Analyses are otherwise the same as for the CBF: whole brain analyses.

Behavioral: Decision-making performance will be analyzed with repeated measures ANOVA on net score, adjusted for education level. Net score is the number of plays on good decks minus bad decks. The behavioral effects of treatment will be analyzed using repeated measures ANOVA on SHAS7, on the psychomotor vigilance task, simple and choice reaction time task, and grooved pegboard task.

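### A drug-induced rise in CBF can lower the BOLD response without any neural change, yet the ASL data enter no BOLD analysis and a BOLD fall is read as reduced brain activity

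*Combined protocol and SAP*

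**What the plan says.** Section I (Specific Aims) makes the same pair of predictions for each drug. For acetate against placebo: "a) increase CBF as measured by arterial spin labeling (ASL); and b) decrease blood oxygen level dependent (BOLD) activity". For alcohol: "orally ingested alcohol jello shots will: a) increase CBF, and b) decrease BOLD activity". Part c of each aim expects both changes to be greater in participants with alcohol use disorder (AUD).

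Section IV.A lists the second preliminary outcome as "Brain activity during decision-making before and after acute alcohol or acetate", and the BOLD model paragraph of section IV.F also describes the interest as drug effects on brain activity in the decision phase.

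Section IV.E, item 2 (Vasomotor effect), recognises the difficulty: "The BOLD signal reflects complex interactions between CBF, cerebral blood volume, and oxygenation". It then says "The fMRI BOLD measurements are insensitive to time lags or shifts in the hemodynamic response of the brain during decision-making", and continues "Therefore in exploratory studies a finite impulse response (FIR) model will be used". The same item states an intention to study vascular differences between acetate and alcohol. Section II says that studying CBF changes after alcohol should help to separate flow from metabolism.

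In section IV.F the main BOLD model uses the canonical haemodynamic response function. For the BOLD regions of interest (ROIs) the outcome is percent signal change, and "The feasibility analyses are the same as CBF: ROI approach", which means a paired t-test for each drug. For the later study the BOLD covariates are education and number of drinks.

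**The concern.** If resting flow rises, the same neural response can produce a smaller BOLD percent change. Prediction b could then follow, in whole or part, from prediction a. The protocol's own background makes this more than a theoretical worry: it describes decoupling of flow from metabolism after alcohol, and offers vasodilation by acetate-derived adenosine as one explanation.

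What is at stake is interpretation. A BOLD fall after acetate or alcohol would be described as less brain activity during decision-making, and its size would go into the planning of the larger study under that label. Part c is exposed in the same way: a larger flow response in AUD participants could by itself yield a larger BOLD fall.

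**Working it through.** **1. What the analysis plan does with flow.** The plan states no figure to reproduce, so the first check is a reading of every BOLD and CBF step.

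| Step (section IV.F unless stated) | Is CBF used? |
|---|---|
| First-level BOLD model: canonical response, motion regressors | No |
| Contrasts: decision or outcome against motor control | No |
| Pilot BOLD ROI test: paired t-test on percent signal change | No |
| Later-study BOLD ROI model: education, drinks per week | No |
| Later-study BOLD whole-brain model: education, drinks per month | No |
| Exploratory FIR model (IV.E item 2) | No |
| CBF ROI and whole-brain analyses | Yes, as an outcome in its own right |

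CBF and BOLD are taken from the same six ROIs at the same two scans, so the data for a paired look already exist.

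**2. Does the motor-control subtraction remove a vascular effect?** Write D and C for the decision and motor-control responses in a region. If altered flow multiplies both by k, the contrast becomes kD − kC = k(D − C). The scale factor stays in the contrast.

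**3. Does FIR remove it?** FIR estimates the response at each lag. It can recover size lost to a delayed or misshapen response, so it is not blind to amplitude. But a response scaled by k is scaled by k at every lag, and nothing in the model says whether k is vascular or neural.

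**4. How large could the effect be?** The documents give neither a BOLD model nor a percentage rise in CBF, so everything here is assumed. Take the calibrated-BOLD relation

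BOLD = M(1 − f^(α−β) m^β),

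with f and m the fractional flow and metabolic responses to the task, and M proportional to F^(α−β), where F is resting CBF on drug divided by resting CBF on placebo. If f and m do not change, the bracket cancels and

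fall in BOLD = 1 − F^(α−β).

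With α from 0.20 to 0.38 and β from 1.3 to 1.5, all four corners are:

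| α / β | α−β | F = 1.05 | F = 1.10 | F = 1.20 |
|---|---|---|---|---|
| 0.38 / 1.3 | −0.92 | 4.4% | 8.4% | 15.4% |
| 0.20 / 1.3 | −1.10 | 5.2% | 10.0% | 18.2% |
| 0.38 / 1.5 | −1.12 | 5.3% | 10.1% | 18.5% |
| 0.20 / 1.5 | −1.30 | 6.1% | 11.7% | 21.1% |

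The ranges are therefore about 4-6%, 8-12% and 15-21%.

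The result depends on what is held fixed. If the absolute rather than the fractional flow response to the task is unchanged (assumed task flow rise 20% or 50%, flow-to-metabolism ratio 2.5), the falls are about 13-15%, 23-27% and 41-47%. In the other direction, a larger fractional flow response on drug would offset the fall.

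**5. Would the pilot's test detect it?** For a paired t-test with n = 15 (the usable control target per aim), two-sided 0.05, and an assumed mean BOLD response of 1 to 4 SDs of the paired difference, a purely vascular 10% fall reaches p < 0.05 in 6.5% to 30% of studies, and a 20% fall in 11% to 82%.

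**The case against.** The strongest reply has four parts.

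- **Direction.** The documents say only that the interactions are complex and give no sign. The decoupling described in section II makes constant coupling doubtful. This stands. A reader might infer that a CBF rise must lower BOLD; the documents do not support that, and the model shows only that it can.
- **Existing intentions.** CBF is analysed as an outcome, and sections II and IV.E state intentions to study flow effects. This also stands, so it would be wrong to say that the ASL data go unused or that the problem was ignored. But neither intention has an analysis step, and the one in IV.E compares acetate with alcohol, not drug with placebo.
- **Wording.** Hypothesis b is worded as BOLD activity, and section IV.F lists the outcome as BOLD signal. A vascular contribution does not make that hypothesis false. The difficulty arises only where the outcome is called brain activity, which sections IV.A and IV.F do.
- **Purpose.** This is a feasibility pilot, and a later study powered on BOLD needs the observed BOLD effect and variance whatever their cause. That is fair for the sample-size arithmetic. It does not cover what the effect is said to mean. Step 5 also shows that a modest vascular fall would often miss significance at n = 15, so one should not suppose that prediction a alone would usually deliver b.

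**Conclusion.** The concern holds in a limited form. The two predictions in each aim may not be independent, because a flow rise can reduce BOLD without neural change, and no planned BOLD analysis looks at flow. For CBF rises of 5%, 10% and 20% the illustrative falls are about 4-6%, 8-12% and 15-21%. They rest on assumed exponents, unchanged metabolic and fractional flow responses, and CBF rises chosen for illustration. The size varies widely under other assumptions, and the sign could be offset.

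The documents do not show that any BOLD decrease seen here would be vascular, nor that the pilot fails in its feasibility purpose. They show that the plan could not tell a reader which explanation applies, and that it does not limit its conclusion accordingly.

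**What to change.** In the BOLD ROI paragraph of section IV.F:

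1. For each ROI and each arm, report the placebo-to-drug BOLD change beside the same ROI's ASL CBF change, with a paired plot and a correlation, labelled descriptive. With 15 pairs, the 95% interval around an observed correlation of zero is about −0.51 to 0.51 (Fisher z: 1.96/√12 = 0.57, back-transformed), so no test should hang on it.
2. A CBF-adjusted BOLD estimate may be added only as a labelled sensitivity analysis, because CBF change is measured after treatment and is imprecise at this sample size.
3. State that a BOLD decrease accompanied by a CBF increase will be reported as a BOLD change that may be partly vascular, not as reduced brain activity, and that the same description goes with the effect size into the larger study.

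Two stronger rules may suggest themselves, and neither should be adopted. Equal shrinkage of the motor-control response in motor or visual cortex would not prove a vascular cause: alcohol may itself suppress visuomotor activity, as the title of the study behind the jello-shot method suggests, and those regions are not among the six ROIs. Survival of the effect after CBF adjustment would not prove a neural cause either: noise in the CBF change weakens the adjustment, and if most participants' CBF rises, the estimate at zero change is an extrapolation.

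The cost is a little extra analysis of data already collected and a more cautious conclusion. No new scans or procedures are needed.

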BOLD fMRI pre-processing: After discarding the first 4 volumes for saturation effects, images will be corrected for movement with a 3-dimensional rigid body transformation. Participants with scan-to-scan head movement >2 mm will be excluded. Motion parameters will be modeled as nuisance variables. Images will be normalized to MNI space using the two step transformation procedure described for MR CBF. Images will be spatially smoothed with a 6 mm full-width-half-maximum isotropic Gaussian kernel, filtered to remove low-frequency fluctuations (128 s high pass filter), and corrected for temporal autocorrelation.

BOLD fMRI: Model specification and contrast of interest: The time series will be predicted by nine regressors, consisting of decision and outcome for each of the four decks, plus motor control. Motion parameters will be modeled as nuisance regressors. The stimulus function will be convolved with the canonical hemodynamic response function (HRF). We are primarily interested in effects of acetate or alcohol on brain activity during the decision phase of the task. The primary outcomes will be the contrast of Decision>motor control baseline and Outcome>motor control baseline. For each participant these contrast maps will be brought to the second level for subsequent ROI and whole-brain analyses.

Regions-of-interest (ROI): ROI and whole brain analyses will be conducted for outcome measures of CBF and fMRI BOLD activity. Six anatomically- defined ROIs will be based on the neural circuitry found to be involved during decision-making on the modified IGT and which overlap with brain regions showing altered signal after acute alcohol (Anderson et al., 2011; Bjork and Gilman, 2014). ROIs will be bilateral ventral striatum (VST), dorsal striatum, insula, and anterior cingulate cortex (ACC), orbitofrontal cortex (OFC), and dorsolateral prefrontal cortex (DLPFC). VST and DST will be manually drawn, based on published landmarks (Mawlawi et al., 2001). For the OFC, insula, ACC, and DLPFC, the automated anatomical labeling atlas (AAL) (Tzourio-Mazoyer et al., 2002) will be used. Figure 3 shows examples of VST=green, DST=orange, OFC=blue, insula=red.

[figure not shown]

Fig 3. Regions of interest

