Statistical Analysis: We have three outcomes of interest: 1) CBF, 2) fMRI BOLD signal during decision-making, 3) behavioral measures. A bio-statistician employed part-time by the Department of Radiology will provide statistical support. The aim of this pilot study is simply to determine the feasibility of performing the experiment and to acquire the necessary data to calculate power needed for a larger study.

CBF: ROI analyses: For this feasibility pilot study, a paired t-test will be used to investigate the effect of acetate and the effect of alcohol separately. In an exploratory manner, drug x time interactions will be examined through descriptive and graphical analyses, though we acknowledge insufficient power to reject the null hypothesis of no interaction. Nevertheless, a noticeable difference in outcomes based on factors of drug or time could provide data to compute power for a larger, more powered study.

To provide context for this pilot, the statistical plan for the later, larger study is included: We will fit a general linear multivariate model with repeated measurements of CBF as the outcomes. Each participant will have 12 repeated measurements (6 ROIs x 2 treatments (acetate and placebo or alcohol and placebo)). Age and number of drinks per week will be included as covariates. MCMC imputation (Li, 1988) will be used to address missing data. A Chi-Muller test will be conducted (Chi and Muller, 2013) for the main effect of treatment (acetate versus placebo or alcohol versus placebo) at any ROI. Residual analysis will be used, and Box-Cox transformations will be considered to account for deviations from multivariate normality. An alpha spending approach will be used to handle multiple comparisons problems, by testing the overall hypothesis of no effect at any region at the $\alpha = 0.04$ level, and then, if we attain significance, testing the treatment effects at each ROI at the $\alpha = 0.01/6$ level. This yields a total Type I error for this aim of $0.05 = 0.04 + 6*(0.01/6)$.

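### Does the 0.05 Type I error given for an aim of the later study understate the error, since each aim also tests BOLD?

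*Combined protocol and SAP*

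**What the plan says.** Section I gives each aim two outcome hypotheses. Aim 1 expects acetate to "a) increase CBF as measured by arterial spin labeling (ASL); and b) decrease blood oxygen level dependent (BOLD) activity"; Aim 2 expects alcohol to "a) increase CBF, and b) decrease BOLD activity".

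In Section IV.F, the paragraph CBF: ROI analyses assigns the pilot a paired t-test for each substance. It then changes subject: "To provide context for this pilot, the statistical plan for the later, larger study is included". For that later study, CBF at six ROIs is modelled jointly. An overall test is made at 0.04, "and then, if we attain significance, testing the treatment effects at each ROI at the" 0.01/6 level. The paragraph closes: "This yields a total Type I error for this aim of" 0.05, shown as 0.04 + 6*(0.01/6).

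The paragraph fMRI BOLD activity: ROI analyses gives BOLD its own model with 12 measurements and otherwise refers back to the CBF approach. Nothing divides alpha between CBF and BOLD.

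On BOLD contrasts, the model-specification paragraph of Section IV.F says "The primary outcomes will be the contrast of Decision>motor control baseline and Outcome>motor control baseline" and "For each participant these contrast maps will be brought to the second level for subsequent ROI and whole-brain analyses". Just before that it says "We are primarily interested in effects of acetate or alcohol on brain activity during the decision phase of the task".

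**The concern.** The 0.05 is computed inside a CBF-only model but labelled as the error of an aim, and both aims in the document contain BOLD as well. If BOLD repeats the rule at full strength, an aim has two overall tests at 0.04, or three if the decision and outcome contrasts are tested separately. The probability of at least one false positive in the aim could then exceed 0.05.

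The possible stake is the later study. This sentence is its only statement of error control for ROI tests, and the pilot is meant to supply that study's sample size. If 0.05 per aim were intended and the levels had to be lowered to achieve it, a sample size planned at 0.04 would be too small.

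**Working it through.** **Inputs.** Overall test 0.04; six ROI tests at 0.01/6, run only after a significant overall test (CBF: ROI analyses). Same rule for BOLD (fMRI BOLD activity: ROI analyses). One or two BOLD contrasts (model specification). The documents give no correlation between CBF and BOLD tests, so independence is an assumption and a range is shown.

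**The plan's figure.** 0.04 + 6 × (0.01/6) = 0.04 + 0.01 = 0.05. It reproduces exactly, as an additive bound for one outcome.

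**One outcome, allowing for the gate.**
- No ROI has an effect: any false positive needs a false overall rejection, so the error is 0.04.
- Some ROI has an effect: the overall null is false, and at most five ROIs can yield a false positive, so the error is at most 5 × 0.01/6 = 0.0083.

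For CBF alone, 0.05 is valid and slightly conservative.

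**CBF plus one BOLD contrast.**

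| True state | Error |
|---|---|
| Neither responds | 1 − 0.96² = 0.0784 if independent; at most 2 × 0.04 = 0.08 |
| One responds, the other does not | at most 0.0083 + 0.04 = 0.0483 |
| Both respond | at most 2 × 0.0083 = 0.0167 |

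**CBF plus two BOLD contrasts as separate families.**

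| True state | Error |
|---|---|
| None responds | 1 − 0.96³ = 0.1153 if independent; at most 0.12 |
| One responds | at most 0.0083 + 2 × 0.04 = 0.0883 |
| Two respond | at most 2 × 0.0083 + 0.04 = 0.0567 |
| All respond | at most 3 × 0.0083 = 0.025 |

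**Dependence.** Two-sided tests at 0.04 with a common correlation were simulated with no effect anywhere (4 million draws per case).

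| Correlation | Two tests | Three tests |
|---|---|---|
| 0 | 0.078 | 0.115 |
| 0.5 | 0.073 | 0.102 |
| 0.8 | 0.063 | 0.080 |
| 0.95 | 0.052 | 0.059 |

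With no effect anywhere, the total stays above 0.05 unless the correlation is extreme.

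**Does anything in the pilot use the 0.05 total?** The pilot's ROI tests are paired t-tests. The whole-brain work is exploratory at an uncorrected threshold. The power paragraph considers a single CBF comparison in 10 people at a Type I error of 0.05; it uses neither the 0.04 gate nor the 0.01/6 level. No sample size for the later study is computed.

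**The case for a change.** The strongest case for a change is that the only aims in the document are Aims 1 and 2. Read literally, the label is therefore wrong. The later study's sample size depends on the level of its overall test, so the ambiguity could carry forward. If 0.05 per aim were met by a 0.025 overall test for each of two outcomes, the sample size for 90% power on that test would rise by about 5–16%. That range assumes a standardised effect of 0.054/0.085 = 0.635 (the alcohol figures in the power paragraph) at one, three or six affected ROIs, ROI correlation 0.3 to 0.8, and two stand-ins for the Chi-Muller test. It is only indicative.

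The mismatch between label and rule stands. The consequence for sample size does not follow. Keeping 0.05 per aim does not force lower levels: with CBF tested first, and one BOLD contrast only after a significant CBF overall test, the existing levels already suffice. The error would be 0.04 if CBF does not respond, at most 0.0483 if it responds and BOLD does not, and at most 0.0167 if both do. A simulation with a Hotelling overall test, 30 participants and ROI correlation 0.3 gave 0.038 to 0.049. The price would be BOLD power when CBF fails. This shows that sharing alpha, ordering the tests or controlling error per outcome is a trade-off, and (a) and (b) are separate hypotheses that many statisticians would control separately.

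The larger figure, 0.115, also rests on a contested reading. Two contrasts are called primary and sent to ROI analysis. Yet the BOLD model has 12 measurements, which six ROIs and two treatments already use up, and the outcome list names only BOLD during decision-making.

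**Conclusion.** The label is loose, and no change to the plan follows. The 0.05 is a sound bound for the CBF ROI tests, and a reader who sees it inside a CBF-only paragraph can take it that way. Read as the error of Aim 1 or Aim 2, it is exceeded with one BOLD contrast only when neither outcome responds: 0.078 if independent, at most 0.08. Once either outcome responds the error is at most 0.0483. Section II itself reports that most studies find alcohol raises CBF, so for Aim 2 the state with no response in either outcome is not the one the protocol expects. The excess reaches 0.115, at most 0.12, only if both contrasts are separate families and nothing responds.

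These figures assume that the overall test holds its 0.04 level. They count ROI tests only; the later study's whole-brain tests and the AUD-versus-control hypotheses are left out and could only add to the total.

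The text is expressly background to a feasibility pilot. Relabelling the sentence would alter no test, sample size or conclusion, and dividing alpha would settle in advance a choice that belongs to the later study's own analysis plan.
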